10.6. Biomarker Analyses

All biomarker measurements will be listed, tabulated, and where appropriate, plotted. Results of biomarker and pharmacodynamic analyses may be presented in a separate report. Planned analyses are based on the availability of clinically valid assays and may be deferred if emerging study data show no likelihood of providing useful scientific information.

Associations between baseline levels and changes from baseline in select markers and clinical response (CD38 expression, EBV-DNA quantification and other biomarkers PK/pharmacodynamic modeling) will be explored. Exploratory genetic analyses will be summarized in separate technical reports.

Results will be presented in a separate report.

10.7. Pharmacokinetic/Pharmacodynamic Analyses

If sufficient data are available, then other pharmacokinetic/pharmacodynamic modeling may be performed, including exploring the relationship between serum concentrations of daratumumab and endpoints of clinical efficacy and safety. Disease-related or mechanism-based biomarkers will be also explored, such as plasma EBV-DNA, blood NK cell counts, and tissue CD38 expression. If performed, details and results of the analysis will be presented in a separate report.

10.8. Safety Analyses

Adverse Events

The verbatim terms used in the eCRF by investigators to identify AEs will be coded using the Medical Dictionary for Regulatory Activities (MedDRA). All reported AEs with onset during the Treatment Phase (ie, treatment-emergent AEs, and AEs that have worsened since baseline) will be included in the analysis. For each AE, the percentage of subjects who experience at least 1 occurrence of the given event will be summarized by treatment group.

Summaries, listings, datasets, or subject narratives may be provided, as appropriate, for those subjects who die, who discontinue treatment due to an AE, or who experience a severe or an SAE.

Clinical Laboratory Tests

Laboratory data will be summarized by type of laboratory test. Reference ranges and markedly abnormal results (specified in the Statistical Analysis Plan) will be used in the summary of laboratory data. Descriptive statistics will be calculated for each laboratory analyte at baseline and for observed values and changes from baseline at each scheduled time point. Changes from baseline results will be presented in pre- versus posttreatment cross-tabulations (with classes for below, within, and above normal ranges). Frequency tabulations of the abnormalities will be made. A listing of subjects with any laboratory results outside the reference ranges will be provided. A listing of subjects with any markedly abnormal laboratory results will also be provided.

Parameters with predefined NCI-CTCAE version 4.03 toxicity grades will be summarized. Change from baseline to the worst toxicity grade experienced by the subject during the study will be provided as shift tables. Worst toxicity grade during treatment will be presented, according to NCI-CTCAE (version 4.03). Clinical relevant changes (ie, causing a treatment intervention or need for concomitant therapy) will be also recorded on the AE eCRF. All other lab abnormalities need not be recorded as AEs.

Electrocardiogram (ECG)

Electrocardiogram data will be summarized by ECG parameter. Descriptive statistics will be calculated at baseline and for observed values and changes from baseline at each scheduled time point. Frequency tabulations of the abnormalities will be made.

Vital Signs

Descriptive statistics of temperature and blood pressure (systolic and diastolic) values and changes from baseline will be summarized at each scheduled time point. The percentage of subjects with values beyond clinically important limits will be summarized.

Physical Examination

Descriptive statistics of changes from baseline will be summarized at each scheduled time point.

Physical examination findings will be summarized at each scheduled time point. Descriptive statistics will be calculated at baseline and for observed values and changes from baseline at each scheduled time point. Frequency tabulations of the abnormalities will be made.

10.9. Interim Analysis

The study is designed with an interim analysis performed at the end of stage 1 when approximately 15 subjects have received at least one dose of study drug and had at least one post-baseline disease evaluation. Enrollment may be put on hold pending the decision of interim analysis unless the decision is clear based on available data before the interim analysis. The purpose of the interim analysis is to evaluate efficacy and safety data in stage 1 and facilitate the early preparation for the next step of development. The totality of efficacy (ORR), safety, and biomarker data will be analyzed at interim. The futility criterion of ORR is defined as at most 1 out of 15 subjects have achieved CR/PR after stage 1. This futility boundary is considered non-binding. Study may be terminated if the futility criteria are met or supported by the totality of data including biomarker and safety data.

In addition, at interim, the association between daratumumab activity and CD38 expression level will be explored. If a strong association between daratumumab activity and CD38 expression level is confirmed by emerging data or a low response rate is observed from stage 1 data due to low CD38 expression levels, then an enrichment strategy may be applied for stage 2 to mitigate the risk of low responses possibly attributed to low CD38 expression. The final analysis may be adjusted accordingly (eg, primary analysis would be based on enriched population) if an enrichment strategy is applied in stage 2.

11. ADVERSE EVENT REPORTING

Timely, accurate, and complete reporting and analysis of safety information from clinical studies are crucial for the protection of subjects, investigators, and the sponsor, and are mandated by regulatory agencies worldwide. The sponsor has established Standard Operating Procedures in conformity with regulatory requirements worldwide to ensure appropriate reporting of safety information; all clinical studies conducted by the sponsor or its affiliates will be conducted in accordance with those procedures.

11.1. Definitions

11.1.1. Adverse Event Definitions and Classifications

Adverse Event

An AE is any untoward medical occurrence in a clinical study subject administered a medicinal (investigational or non-investigational) product. An AE does not necessarily have a causal relationship with the treatment. An AE can therefore be any unfavorable and unintended sign (including an abnormal finding), symptom, or disease temporally associated with the use of a medicinal (investigational or non-investigational) product, whether or not related to that medicinal (investigational or non-investigational) product. (Definition per International Conference on Harmonisation [ICH])

This includes any occurrence that is new in onset or aggravated in severity or frequency from the baseline condition, or abnormal results of diagnostic procedures, including laboratory test abnormalities.

Note: The sponsor collects AEs starting with the signing of the ICF (refer to Section 11.3.1, All AEs, for time of last AE recording).

Serious Adverse Event

An SAE based on ICH and EU Guidelines on Pharmacovigilance for Medicinal Products for Human Use is any untoward medical occurrence that at any dose:

- Results in death
- Is life-threatening
(The subject was at risk of death at the time of the event. It does not refer to an event that hypothetically might have caused death if it were more severe.)
- Requires inpatient hospitalization or prolongation of existing hospitalization
- Results in persistent or significant disability/incapacity
- Is a congenital anomaly/birth defect
- Is a suspected transmission of any infectious agent via a medicinal product
- Is Medically Important*

*Medical and scientific judgment should be exercised in deciding whether expedited reporting is also appropriate in other situations, such as important medical events that may not be immediately life threatening or result in death or hospitalization but may jeopardize the subject or may require intervention to prevent 1 of the other outcomes listed in the definition above. These should usually be considered serious.

If a serious and unexpected AE occurs for which there is evidence suggesting a causal relationship between the study drug and the event (eg, death from anaphylaxis), the event must be reported as a serious and unexpected suspected adverse reaction even if it is a component of the study endpoint (eg, PD).

Unlisted (Unexpected) Adverse Event/Reference Safety Information

An AE is considered unlisted if the nature or severity is not consistent with the applicable product reference safety information. For daratumumab, the expectedness of an AE will be determined by whether or not it is listed in the IB.¹⁸

Adverse Event Associated With the Use of the Drug

An AE is considered associated with the use of the drug if the attribution is possible, probable, or very likely by the definitions listed in Section 11.1.2, Attribution Definitions.

11.1.2. Attribution Definitions

Not Related

An AE that is not related to the use of the drug.

Doubtful

An AE for which an alternative explanation is more likely, eg, concomitant drug(s), concomitant disease(s), or the relationship in time suggests that a causal relationship is unlikely.

Possible

An AE that might be due to the use of the drug. An alternative explanation, eg, concomitant drug(s), concomitant disease(s), is inconclusive. The relationship in time is reasonable; therefore, the causal relationship cannot be excluded.

Probable

An AE that might be due to the use of the drug. The relationship in time is suggestive (eg, confirmed by dechallenge). An alternative explanation is less likely, eg, concomitant drug(s), concomitant disease(s).

Very Likely

An AE that is listed as a possible adverse reaction and cannot be reasonably explained by an alternative explanation, eg, concomitant drug(s), concomitant disease(s). The relationship in time is very suggestive (eg, it is confirmed by dechallenge and rechallenge).

11.1.3. Severity Criteria

An assessment of severity grade will be made using the following general categorical descriptors:

Mild: Awareness of symptoms that are easily tolerated, causing minimal discomfort and not interfering with everyday activities.

Moderate: Sufficient discomfort is present to cause interference with normal activity.

Severe: Extreme distress, causing significant impairment of functioning or incapacitation. Prevents normal everyday activities.

The investigator should use clinical judgment in assessing the severity of events not directly experienced by the subject (eg, laboratory abnormalities).

11.2. Special Reporting Situations

Safety events of interest on a sponsor study drug that may require expedited reporting or safety evaluation include, but are not limited to:

- Overdose of a sponsor study drug
- Suspected abuse/misuse of a sponsor study drug
- Accidental or occupational exposure to a sponsor study drug
- Medication error involving a sponsor product (with or without subject/patient exposure to the sponsor study drug, eg, name confusion)
- Exposure to a sponsor study drug from breastfeeding.

Special reporting situations should be recorded in the eCRF. Any special reporting situation that meets the criteria of an SAE should be recorded on the SAE page of the eCRF.

11.3. Procedures

11.3.1. All Adverse Events

All AEs and special reporting situations, whether serious or non-serious, will be reported from the time a signed and dated ICF is obtained until 30 days after the last dose of study drug, unless the subject withdraws consent for study participation, or starts subsequent anticancer therapy. For subjects who have received additional treatment with therapeutic intent for NKTCL during the AE reporting period, only AEs that are considered to be possibly, probably, or definitely related to study drug must be reported (unless the subject has been withdrawn from the study). Serious adverse events (SAEs), including those spontaneously reported to the investigator within 30 days after the last dose of study drug, must be reported using the SAE Form. The sponsor will evaluate any safety information that is spontaneously reported by an investigator beyond the time frame specified in the protocol.

All AEs, regardless of seriousness, severity, or presumed relationship to study drug, must be recorded using medical terminology in the source document and the eCRF. Whenever possible, diagnoses should be given when signs and symptoms are due to a common etiology (eg, cough, runny nose, sneezing, sore throat, and head congestion should be reported as "upper respiratory infection"). Investigators must record in the eCRF their opinion concerning the relationship of the AE to study therapy. All measures required for AE management must be recorded in the source document and reported according to sponsor instructions.

The sponsor assumes responsibility for appropriate reporting of AEs to the regulatory authorities. The sponsor will also report to the investigator (and the head of the investigational institute where required) all suspected unexpected serious adverse reactions (SUSARs).

For all studies with an outpatient phase, including open-label studies, the subject must be provided with a "wallet (study) card" and instructed to carry this card with them for the duration of the study indicating the following:

- Study number
- Statement, in the local language(s), that the subject is participating in a clinical study
- Investigator's name and 24-hour contact telephone number
- Local sponsor's name and 24-hour contact telephone number (for medical staff only)
- Site number
- Subject number
- Any other information that is required to do an emergency breaking of the blind.

Progression of the disease under study is not considered an AE (or SAE), even if it results in death during the AE reporting period. If a clinical sign or symptom or a laboratory test abnormality is observed in a subject with PD, but is not related to PD under study, then the usual AE reporting requirements apply.

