Concomitant therapy	continuous from the time of signing of ICF until 30 days after last dose of study drug; See Section 7 for detailed instructions.								
Adverse events	continuous from the time of signing of ICF until 30 days after last dose of study drug; See Section 11 for detailed instructions.								

Abbreviations: Anti-HBc= antibodies to hepatitis B core antigen; Anti-HBs= antibodies to hepatitis B surface antigen; C=cycle; COPD=chronic obstructive pulmonary disease; CR=complete response; CT=computed tomography; D=day; DNA=deoxyribonucleic acid; EBV=Epstein Barr virus; ECG=electrocardiogram; ECOG=Eastern Cooperative Oncology Group; EoT=end-of-treatment; FEV1= forced expiratory volume (in 1 second); FFPE= formalin-fixed, paraffin-embedded; FU=follow-up; HBV=hepatitis B virus; HBsAg= hepatitis B surface antigen; IAT=indirect antiglobulin test; ICF=informed consent form; IRR=infusion related reaction; MRI=magnetic resonance imaging; PCR=polymerase chain reaction; PD=progressive disease; PET=positron emission tomography; PK=pharmacokinetics; Q8 weeks=every 8 weeks; SIPP=site investigational product procedures manual; Wk=week.

Footnotes:

- a. Diagnosis of NKTCL is performed by the local hospital and the pathology report will be verified by the sponsor before enrolment.
- b. Women of childbearing potential only, within 14 days of C1D1.
- c. Fresh biopsy within 21 days prior to C1D1 or archived sample FFPE sample (block or slides) should be sent to sites prior to C1D1.
- d. For Cycle 1 Day 1, no need to repeat tests if they have been performed within the past 5 days. Testing may be performed up to 2 days before other infusion days. Results of hematology tests must be evaluated before each study drug administration. Perform at additional time points, as clinically indicated. To be done by local lab. Refer to Section 8.6 for parameters to be tested.
- e. If a subject's weight changes by more than 10% from baseline, the dose of the study drug will be re-calculated.
- f. ECOG assessment should be obtained prior to dosing of daratumumab on Day 1 of each cycle. ECOG is also required to be collected in every disease evaluation assessment date.

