11.3.2. Serious Adverse Events

All SAEs occurring during the study must be reported to the appropriate sponsor contact person by study-site personnel within 24 hours of their knowledge of the event.

Information regarding SAEs will be transmitted to the sponsor using the SAE Form, which must be completed and signed by a physician from the study site, and transmitted to the sponsor within 24 hours. The initial and follow-up reports of an SAE should be made by facsimile (fax).

All SAEs that have not resolved by the end of the study, or that have not resolved upon discontinuation of the subject's participation in the study, must be followed until any of the following occurs:

- The event resolves
- The event stabilizes
- The event returns to baseline, if a baseline value/status is available
- The event can be attributed to agents other than the study drug or to factors unrelated to study conduct
- It becomes unlikely that any additional information can be obtained (subject or health care practitioner refusal to provide additional information, lost to follow-up after demonstration of due diligence with follow-up efforts)

Suspected transmission of an infectious agent by a medicinal product will be reported as an SAE. Any event requiring hospitalization (or prolongation of hospitalization) that occurs during the course of a subject's participation in a study must be reported as an SAE, except hospitalizations for the following:

- Hospitalizations not intended to treat an acute illness or AE (eg, social reasons such as pending placement in long-term care facility)
- Surgery or procedure planned before entry into the study (must be documented in the eCRF). Note: Hospitalizations that were planned before the signing of the ICF, and where the underlying condition for which the hospitalization was planned has not worsened, will not be considered SAEs. Any AE that results in a prolongation of the originally planned hospitalization is to be reported as a new SAE.
- For convenience the investigator may choose to hospitalize the subject for the duration of the treatment period.

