2.1. Visit Windows

Any analysis that uses time-to-event data will be based on the exact determination of time from first dose of Dara to the date of the event. For the calculation of time-to-event and duration-of-event variables, the difference between the start date and the end date plus 1 day will be used.

For analyses of data by cycle, if data are collected by date (ie, AE onset), the corresponding study evaluations will be assigned to actual sequential cycles, which are derived from the study treatment administration data. The start date of a particular cycle is defined as the date of the first Dara, and the end date of a cycle is the start date of the next cycle minus 1. For the last cycle, the end date is defined as the end of treatment visit date or the minimum of last study treatment date plus 30 days or subsequent anticancer therapy minus 1 day, if the end of treatment visit date is not available.

In general, if data (e.g., laboratory and vital sign, etc.) are collected by cycle, the nominal cycle will be used to summarize data.

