6. SAFETY

Unless specifically stated, the observations that occurred during treatment period (i.e., within 30 days from the last study drug dosing) will be used for safety analyses. All observations will be presented in listings.

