6.1. Adverse Events

The verbatim terms used in the CRF by investigators to identify adverse events will be coded using the most current version of the Medical Dictionary for Regulatory Activities (MedDRA). Toxicities will be graded for severity according to CTCAE, Version 4.03. All reported adverse events with onset during the treatment period (ie, treatment-emergent adverse events, and adverse events that have worsened since baseline, and within 30 days from the last dose) will be included in the analysis and reported using descriptive statistics and frequency tabulations.

The incidence of TEAEs will be summarized overall, by MedDRA system organ class (SOC) and preferred term, by toxicity grade, and by relationship to study treatment administration.

Specifically, the following will be summarized or listed:

- All adverse events
- Grade 3 or higher adverse events
- Serious adverse events
- Adverse events leading to discontinuation of treatment
- Treatment-emergent infusion related reactions
- Adverse events leading to treatment cycle delays or dose modifications
- Adverse events leading to death

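### Protocol 11.3.1 is ambiguous about adverse events after subsequent anticancer therapy, and the SAP safety windows have no cut at that point, so late events are collected unevenly and effects of the new therapy can be counted as daratumumab treatment-emergent

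*Protocol*

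**What the plan says.** **Collection.** Protocol 11.3.1 has all AEs, serious ones included, reported from consent to 30 days after the last dose "unless the subject withdraws consent for study participation, or starts subsequent anticancer therapy". The next sentence covers subjects who receive additional treatment for NKTCL within the reporting period: for them "only AEs that are considered to be possibly, probably, or definitely related to study drug must be reported". The following paragraph of 11.3.1 asks for every AE to be recorded in the eCRF whatever its presumed cause. The adverse events row of the Time and Events Schedule reads "continuous from the time of signing of ICF until 30 days after last dose of study drug; See Section 11 for detailed instructions".

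**Serious events.** Protocol 11.3.2 says "All SAEs occurring during the study must be reported to the appropriate sponsor contact person". It states no exception for subsequent therapy.

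**Attribution scale.** Protocol 11.1.2 defines not related, doubtful, possible, probable and very likely. Protocol 11.1.1 treats the last three as drug-associated. *Definitely*, the word used in 11.3.1, is not a category.

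**Analysis.** SAP 6 states that "observations that occurred during treatment period (i.e., within 30 days from the last study drug dosing) will be used for safety analyses". SAP 6.1 starts from "All reported adverse events with onset during the treatment period" and includes onset up to 30 days after the last dose, with no condition on causality. SAP 6.3 runs laboratory shift tables to 30 days after the last dose or the end-of-treatment (EoT) visit, whichever is later. Protocol 10.8 instead analyses AEs with onset in the Treatment Phase, which Protocol 3.1 ends at study drug discontinuation.

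**The one safety-related cut at new therapy.** SAP 2.1 ends the last cycle at "the minimum of last study treatment date plus 30 days or subsequent anticancer therapy minus 1 day", but only for assigning data to cycles and only when the EoT visit date is missing.

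**The concern.** Safety tables can be interpreted only if the period over which events are collected matches the period over which they are counted. Here the collection rule changes when new anticancer therapy starts, in a way the text leaves open, while the counting rule takes no notice of it.

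Two errors can follow, in opposite directions. Non-serious events unrelated to daratumumab may go uncollected after a switch, while the subject still counts as fully observed to day 30. Events and laboratory changes caused by the new treatment, if they reach the database, are tabulated as daratumumab treatment-emergent. If only related events are collected after a switch, the related share among late events is also raised by construction.

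The trial has a single arm and 32 subjects in its two main stages. No control group absorbs such errors, and a few misassigned Grade 3 or higher events would visibly change a rate.

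**Working it through.** The plan gives no figure to reproduce. The check sets the rules side by side for one subject and then sizes the exposed time under stated assumptions.

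**1. One subject.** Suppose new therapy starts on day 14 after the last dose and the event or sample falls on day 20, after study drug discontinuation.

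| Item on day 20 | 11.3.1, sentence 1 alone | 11.3.1, both sentences joined | 11.3.2 | SAP |
|---|---|---|---|---|
| Non-serious AE, unrelated | not reported | not reported | not applicable | counted if reported (6.1) |
| Non-serious AE, related | not reported | reported | not applicable | counted if reported (6.1) |
| Serious AE, unrelated | not reported | not reported | reported | counted if reported (6.1) |
| Laboratory value | no rule | no rule | not applicable | in shift and worst-grade tables (6.3) |

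Two rows turn on which text a site follows: the related non-serious event and the unrelated serious event. The unrelated serious event reported under 11.3.2 and the laboratory value then enter daratumumab tables although new therapy had already begun. Protocol 10.8 would exclude the AEs in all three AE rows, because their onset is after the Treatment Phase.

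**2. Attribution word.** The drug-associated categories in 11.1.1 are possible, probable and very likely. Those in 11.3.1 are possibly, probably and definitely. Taken literally, the related-only rule leaves out the strongest category on the scale.

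**3. Laboratory window.** Protocol 3.1 sets the EoT visit within 30 days of the last dose with a 7-day window, so it can fall on day 30 + 7 = 37. For the subject above, laboratory values over up to 37 − 14 = 23 days after the switch could set the worst grade.

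**4. Size (illustration only).** Let *f* be the share of subjects who start new therapy within 30 days of the last dose, and *s* the day they start. The documents give neither.

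- Share of a switcher's 30-day window without all-AE collection: (30 − s)/30.
  - s = 7: 23/30 = 77%
  - s = 14: 16/30 = 53%
  - s = 21: 9/30 = 30%
- Share of all post-dose person-time: f × (30 − s)/30.
  - Low: 0.2 × 9/30 = 6%
  - Middle: 0.5 × 16/30 = 27%
  - High: 0.8 × 23/30 = 61%

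If 11.3.1 is read as stopping, related non-serious events in that time are lost as well. If the sentences are joined, only unrelated ones are. Events before the switch are unaffected under either reading.

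**The case against.** The strongest reply is that 11.3.1 can be read as a whole: all events until new therapy, then related events to day 30. If reporting simply stopped, the second sentence would have almost nothing to govern. On that reading the AEs available to SAP 6.1 are largely the right ones already, because it counts only reported events and cannot add events that were never collected. This stands in part. A reader might infer a flat contradiction within 11.3.1, and the documents do not support that; it is an ambiguity. But the text does not state the joined reading, and joining the sentences settles neither the serious-event rule in 11.3.2 nor the laboratory tables.

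A reader might also infer three competing windows, with the Time and Events Schedule as the third. That does not hold: the schedule defers to Section 11, and related-only is a filter on events, not a window.

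The serious-event provisions limit the loss of serious events. However, sentence 1 of 11.3.1 expressly covers serious events, so the two sections still need reconciling. Protocol 8.1.3 asks sites to try to hold the EoT visit before subsequent treatment starts. That reduces the laboratory problem but does not remove it, because it is not a requirement.

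It is also tempting to treat an early switch as the usual way off study. The documents give no rate. Inclusion criterion 3.1 requires subjects judged unsuitable for other treatment modalities, which points the other way. On the other side, SAP 2.7.5 has a rule for therapy starting in the same month as the last dose, so early switching is at least foreseen.

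**Conclusion.** The point holds as an ambiguity in collection combined with an analysis window that does not match it. For subjects who switch within 30 days of the last dose, ascertainment of late events is inconsistent, and reported toxicity or laboratory changes from the new therapy can be counted as daratumumab treatment-emergent. Following the SAP as written produces that result for laboratory values, and for unrelated serious events reported under 11.3.2.

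The effect is confined to the interval from the start of new therapy to day 30 for AEs, or to the EoT visit if later for laboratory grades. On-treatment safety results and the primary endpoint are untouched. The number of subjects affected cannot be derived from the documents; the 6% to 61% of post-dose person-time rests wholly on assumed *f* of 20% to 80% and *s* of day 7 to 21.

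SAP 2.1 might be taken to show that the SAP already makes the needed cut. It does not: that rule is a fallback for assigning data to cycles. The change is worth making because it is small and prevents a misattribution that a single-arm trial cannot otherwise detect.

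**What to change.** 1. **Protocol 11.3.1.** State one rule: all AEs until subsequent anticancer therapy starts, then drug-related AEs to day 30 after the last dose. Replace *definitely* with *very likely*. Make the recording paragraph consistent with this, and reconcile the rule with 11.3.2 by stating whether serious events are exempt from it.
2. **SAP 6 and 6.1.** Define treatment-emergent as first dose to the earlier of 30 days after the last dose or the day before subsequent anticancer therapy, plus later drug-related AEs to day 30.
3. **SAP 6.3.** Exclude laboratory values taken on or after the start of subsequent therapy from the shift and worst-grade tables.
4. **Protocol 10.8.** Replace onset in the Treatment Phase with the same window.

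The cost is a few sentences in each document. Some late unrelated events and laboratory values would appear only in listings, which SAP 6 already provides for all observations. Events after new therapy would be related-only by design, so they should be identified separately from earlier events; otherwise the related share among late events would still mislead.
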